## 4.6 Analysis of Secondary Objectives

## 4.6.1 Efficacy (Secondary)

All the secondary endpoints POM at day 3 and 8, Karlsson score, tenderness, swelling and diary assessments (SPID and TOTPAR) will be analyzed using an ANCOVA model with treatment and center as fixed effect, baseline assessment for the corresponding endpoints as covariate. Treatment differences and two-sided 95% CI will be presented.

The secondary efficacy analyses will be performed and also be listed on mITT and PP population.

- Change from baseline of POM (CRF page: Pain on Movement; VAS score will be obtained from VASSCRL) on VAS on days 3 and 8 respectively (PPD).
- Tenderness measured by pressure algometry on days 3, 5 and 8 which will be analysed using change from baseline and difference between the measurement in injured area (CRF page: Tenderness; measurement for study ankle : QS\_INJA) and contralateral area (CRF page: Tenderness; measurement for study ankle : QS\_CLTA) (**PPD**)...
- Change from baseline Ankle Joint Function (Karlsson Scoring Scale; CRF page: Ankle Joint Function: Variable : Total Score KSSTS) on days 3, 5 and 8 (PPD)...
- Circumference measurement of swelling on days 3, 5 8 which will be analysed using change from baseline in circumference of affected ankle and comparison to non-affected ankle by Figure of Eight method (CRF Page:Ankle swelling; Variables: FOEMINSC and FOEMCASC respectively.) (PPD ;)..
- Pain Intensity and Pain Relief (CRF Page: Subject Diary(Day 1/5) ; variables will used to calculate the Pain Intensity and Pain Relief are DPI and DPR respectively for each timepoint (DSTMPT))
- Pain Intensity (PPD
  - Pain intensity will be analysed based on the Sum of Pain Intensity Difference (SPID). SPID is defined as from 0 -24 hours post first dose corresponding to day 1 and from 0-24 hours post first dose corresponding to day 5.
  - SPIDt=>PIDt(timet-timet-1)(h), where, PIDt=pain intensity score (DPI from CRF page corresponding to day); timet=time in hours post first dose

GlaxoSmithKline Consumer Healthcare Confidential

Page 23 of 36

211206

Statistical Reporting and Analysis plan Draft V2.0 20JAN2021

- Pain Relief (**PPD** 
  - Pain relief will be analysed based on the Total Pain Relief (TOTPAR). TOTPAR is defined as from 0-24 hours post first dose corresponding to day 1 and from 0-24 hours post first dose corresponding to day 5.
  - TOTPAR=∑Rt(timet-timet-1), where Rt =pain relief score (DPR from CRF page corresponding to day)

#### 4.6.2 Pharmacokinetic (Secondary)

Not Applicable

## 4.7 Analysis of Safety

#### 4.7.1 Adverse Events and Serious Adverse Events

Adverse events (AE) recorded during the study will be mapped to a system organ class (SOC) and preferred term (PT) using the current medical dictionary for regulatory activities (MedDRA).

Treatment emergent adverse events (TEAEs) are defined as new AEs that occur on or after the date/time of the first administration of study product or worsens if AE started prior to start of first administration.

Summary of all TEAE (**PPD**) will be presented with the following information –

- Number and % of subjects with at least one TEAE
- Time at risk in weeks (Patient-weeks [PW=YY.Y] = sum of the time on study in weeks=[(sum of the time on study in days)/7]
- Number of adverse events (cases)
- Exposure-Adj-TEAE in 100 weeks= 100\*(number of patients with AE/sum of days at risk for AE) x 7days/weeks. It represents the number of events occurring in 100 Patient-Weeks
- P-value (P-value will be obtained from Poisson regression model with number of subjects with AE as dependent variable, treatment and treatment as independent fixed effect. logarithm of time at risk will be considered as offset. Risk ratio and 95% confidence interval will also be presented along with the p-value.)

Refer Appendix 4 for sample SAS code.

All other TEAE will be presented with the following information -

• Number of cases

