#### SAS code for Rescue Medication Analysis:

where,

1. nAE is number of patients with TEAE.

GlaxoSmithKline Consumer Healthcare Confidential

Page 33 of 36

211206

Statistical Reporting and Analysis plan Draft V2.0 20JAN2021

2. Logt=Logarithim (time to first AE or time at risk)( where time at risk = sum of (if a subject experienced an event it is time to first AE, if the subject did not experience event, it is time on study))

GlaxoSmithKline Consumer Healthcare Confidential Page **34** of **36** 

[figure not shown]

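### The exposure-adjusted TEAE rate in SAP 4.7.1 counts subjects but is described as events, and its time at risk is defined differently in 4.7.1 and Appendix 4

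*SAP*

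**What the plan says.** SAP 4.7.1 lists the rows of the overall TEAE summary. Three matter here.

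- **Time at risk.** Patient-weeks are given as "sum of the time on study in weeks=[(sum of the time on study in days)/7", with no stop at a first AE.
- **Exposure-adjusted rate.** This is 100 times "number of patients with AE/sum of days at risk for AE) x 7days/weeks". The next sentence interprets it: "It represents the number of events occurring in 100 Patient-Weeks".
- **Model.** A Poisson regression takes the number of subjects with an AE as outcome and log time at risk as offset. Its output is called a risk ratio, with a 95% CI and p-value.

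The count of AE cases is a separate row and does not enter the rate.

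Section 4.7.1 refers to Appendix 4 for the code. The notes there define the outcome as the number of patients with a TEAE and the offset as "Logt=Logarithim (time to first AE or time at risk", and explain time at risk as: "if a subject experienced an event it is time to first AE, if the subject did not experience event, it is time on study". The code itself is not shown and the notes sit under the rescue-medication heading. They are read here as the AE model notes because they name TEAEs and time to first AE.

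**The concern.** A count of subjects is not a count of events unless nobody has more than one TEAE, so the formula and the sentence that interprets it cannot both hold in general. The two definitions of time at risk differ for every subject with an event: one counts the whole time on study, the other only the time up to the first AE. Neither document reconciles them.

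Two programmers following the SAP could therefore print different rates. A table could also show patient-weeks that reproduce neither the rate beside them nor the model offset. The rate and the Poisson ratio bear on the secondary safety endpoint (number, incidence and severity of AEs), and the ratio is the only between-arm AE comparison described in 4.7.1. Protocol 12.2.7 plans numbers and percentages of subjects, so it does not settle which definition was meant.

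**Working it through.** The documents state no AE rate, count or ratio, so there is no figure to reproduce.

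**Units.** The conversion is sound: 10 subjects in 1,050 days gives 100 × (10/1,050) × 7 = 6.67 per 100 patient-weeks, the same as 10 subjects in 150 weeks.

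**Inputs.** From the documents: about 300 randomized 1:1 (SAP 1.4 and 1.1), so 150 per arm. Assumed: 8 days on study for everyone, 3 days contributed to first AE by each affected subject, and the incidences and AEs per affected subject below.

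**Formulas**, per 100 patient-weeks:

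- A (4.7.1 time): 700 × subjects with an AE / total days on study
- B (Appendix 4 time): 700 × subjects with an AE / (days on study of unaffected subjects + days to first AE of affected subjects)
- E (what the label describes): 700 × number of AEs / total days on study

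**10% affected (15 of 150); total days 150 × 8 = 1,200**

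- A = 700 × 15 / 1,200 = 8.75
- B = 700 × 15 / (135 × 8 + 15 × 3) = 10,500 / 1,125 = 9.33
- E at 1 AE each = 700 × 15 / 1,200 = 8.75. A equals E and B is above it.
- E with 16 AEs (one subject has two) = 700 × 16 / 1,200 = 9.33. B equals E.
- E at 1.5 AEs each = 700 × 22.5 / 1,200 = 13.1. A is 33% too low (8.75/13.125 = 0.67) and B is 29% too low (9.33/13.125 = 0.71).

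**20% affected (30 of 150), 2 AEs each**

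- A = 700 × 30 / 1,200 = 17.5
- B = 700 × 30 / (120 × 8 + 30 × 3) = 21,000 / 1,050 = 20.0
- E = 700 × 60 / 1,200 = 35.0. A is 50% too low and B is 43% too low.

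**Denominator alone.** B/A = 9.33/8.75 = 1.07 at 10% affected and 20.0/17.5 = 1.14 at 20%.

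**Effect on the ratio**, now with 7 days on study and the first AE at day 2 to day 3.5. With 10% against 5% affected, time on study gives 2.00. Time to first AE gives (15/997.5)/(7.5/1,023.75) = 2.05 at day 3.5 and (15/975)/(7.5/1,012.5) = 2.08 at day 2. With 30% against 15% affected, time on study gives 2.00 and time to first AE gives 2.18 to 2.27.

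**What the model estimates.** With a subject count as outcome and log time as offset, it estimates a ratio of subject rates per unit time, that is, a rate ratio. Over equal time on study this equals the risk ratio numerically (2.00 above). With time to first AE it does not.

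**The case against.** The strongest reply is that a coherent reading exists. The rate's own denominator is worded as days at risk for AE, not time on study. If that phrase takes its meaning from Appendix 4, then numerator, denominator, model outcome and offset together form a standard first-event incidence rate. Only the patient-weeks row and one descriptive sentence would need editing. This stands as far as it goes: the method is usable and the fault is one of labelling and consistency. It does not remove the fault, because the only definition of time at risk in 4.7.1 is time on study, and the events label is wrong under either denominator.

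It also stands that the safety endpoint is still reported. Subjects, percentages and AE cases have their own rows in the same summary, and further tables give them by system organ class, preferred term and intensity.

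Three stronger readings are tempting, and the documents do not support them.

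- A reader might infer that the table understates the event rate whenever any subject has more than one AE. With Appendix 4 time that fails: 15 subjects with 16 events give 9.33 either way.
- A reader might infer that the printed table will certainly carry a mismatched denominator. The code and table shells are not visible, so the documents show only that the text permits it.
- A reader might see a misspecified model in "treatment and treatment as independent fixed effect". It is most likely a typing slip, and a duplicated term does not change the fit.

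**Conclusion.** The point holds as a minor inconsistency in a supplementary safety summary. The planned figure is a rate of subjects with at least one TEAE, described as an event rate, and its time at risk has two incompatible definitions.

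The size of the mislabelling is set mainly by the number of AEs per affected subject, which the documents do not give. In the worked cases it runs from no understatement at one AE each, through 29–33% at 10% affected with 1.5 AEs each, to 43–50% at 20% affected with 2 AEs each. The choice of denominator matters less: about 7% on the rate at 10% affected, and about 4% or less on the ratio with 10% against 5% affected.

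TEAE counts and percentages, the case count and the primary analysis are unaffected.

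**What to change.** 1. Use one first-event definition: subjects with a first TEAE divided by the sum of time to first TEAE, or to end of observation for subjects without one. Apply it in the patient-weeks row, the rate and the Poisson offset, and make 4.7.1 and Appendix 4 agree.
2. Label the rate as subjects with at least one TEAE per 100 patient-weeks at risk, and delete the sentence that calls it a number of events.
3. Call the model output a rate ratio with its 95% CI, and name treatment once.
4. If an event rate is wanted, add a separate row of total TEAEs divided by total time on study, and print that time as its denominator.
5. State when observation ends. Protocol 10.3.1 collects AEs until 28 days after the last application, so counting about 35 days (7 + 28) instead of 7 would divide a time-on-study rate by about 5.

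The cost is SAP wording, table labels and minor programming. No new data are needed.

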#### GlaxoSmithKline Consumer Healthcare Confidential

Page 24 of 36

- Number of subjects with AE
- % of subjects with AE

All the AE information will be taken from the Adverse Event CRF page.

The following summary tables and listings will be presented by treatment group and overall for safety population:

- Table of TEAEs by System Organ Class and Preferred Term (**PPD**
- Table of Serious TEAEs by System Organ Class and Preferred Term (PPD
- Treatment Emergent Adverse Events by System Organ Class, Preferred Term and Intensity (PPD)
- Treatment Related Treatment Emergent Adverse Events by System Organ Class and Preferred Term by Relationship status (PPD)
- Treatment Emergent Adverse Events by Preferred Term leading to Drug Withdrawal (PPD
  )
- Treatment Related Treatment Emergent Serious Adverse Events by Preferred Term (PPD
  )
- Treatment Emergent Adverse Events Leading to Study Discontinuation by Preferred Term (PPD)
- **PPD** All Treatment Emergent Adverse Events by Preferred Term
- Listing of all AEs (including all subjects: **PPD**) for all safety subjects.
- Listing of all Serious Adverse Events (**PPD**

Additionally, all treatment-emergent adverse events will be listed (PPD).

Deaths occurring during treatment (if any) will be listed by treatment, including the date and study day of death, and the principal cause of death (**PPD**).

#### 4.7.2 Laboratory Tests

Laboratory results will be summerised using safety population. Chemistry and hematology samples will be collected at Visit 1 (Screening/Baseline ) and Visit 4 (Early D/C). The results will be summarized by visit and treatment. Descriptive statistics the mean, standard deviation, median, minimum and maximum values in each treatment group will be presented (PPD

). Shifts in laboratory results for both chemistry and hematology will be presented in tables (**PPD**). Laboratory hematology, chemistry and Urine Pregnancy test parameters will be listed in **PPD** respectively.

GlaxoSmithKline Consumer Healthcare Confidential

Page 25 of 36

211206

Statistical Reporting and Analysis plan Draft V2.0 20JAN2021

As per the protocol following tests will be conducted for chemistry and hematology. Hematology related information should be mapped with Hematology CRF page and blood chemistry related information will be mapped with Chemistry CRF page. For other test Urine Pregnancy CRF page will be used.

| Chemistry               | Hematology             | Other                |
|-------------------------|------------------------|----------------------|
| BUN/Urea/Creatinine     | Hemoglobin             | Urine Pregnancy test |
| Glucose (fasting)       | Hematocrit RBC count   |                      |
| Calcium                 | Platelet count         |                      |
| Sodium                  | WBC cont               |                      |
| Magnesium               | Total Neutrophil (Abs) |                      |
| Potassium               | Eosinophil (Abs)       |                      |
| Total CO2 (Bicarbonate) | Monocytes (Abs)        |                      |
| AST, ALT                | Basophils (Abs)        |                      |
| Direct Bilirubin        | Lymphocytes (Abs)      |                      |
| Indirect Bilirubin      |                        |                      |
| Total Bilirubin         |                        |                      |
| Alkaline Phophatase     |                        |                      |
| Uric acid               |                        |                      |
| Albumin                 |                        |                      |
| Total Protein           |                        |                      |
| PT/INR                  |                        |                      |

Table 4-2Laboratory Tests

Definitions: RBC= Red blood cell; WBC= White blood cells; BUN=Blood urea nitrogen; HIV= Humanimmunodeficiency virus; AST= transaminase; ALT= alanine transaminase; PT/INR= prothrombin time/international normalized ratio;

Urine pregnancy test will be conducted at Visit 1 (Screening/Baseline ) and Visit 4(Early D/C ). Urine pregnancy test will be listed in **PPD**. Unire pregnancy related information will be taken from urine pregnancy test pafe from CRF.

All laboratory results will be listed including data from unscheduled visits. For lab summary and shift tables, the last available record/value for a particular lab test for a subject at a particular visit; will be considered for analysis. In case there are some unscheduled tests (irrespective of schedule visit or not) are conduted in any center due to some safety concerns then those tests will be listed. This information will be gathered from hematology and chemistry CRF page.

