- POM, tenderness, ankle swelling, and ankle joint function (total score and subcategories) will be assessed
- Count and document remaining rescue medication.
- If insufficient rescued medication remains, additional rescue medication may be dispensed
- No rescue medication is allowed within 12 hours of this Visit
- Collect Visit 2 subject diary
- Dispense Visit 3 subject diary and instruct subject about appropriate use

8.2.3 Visit 4 /Day 8 ± 1

Procedures for this visit are also to be completed if the subject terminated the study prematurely.

- Changes in concomitant medication or non-drug treatments/procedures will be documented in the CRF.
- Spontaneous reporting of adverse events and those elicited by asking subjects to respond to a non-leading question such as "How do you feel?" will be assessed and any AEs recorded in the CRF.
- Subject continued eligibility
- The 4 tubes of study medication will be weighed. The weight of each tube will be documented in the CRF
- Collect remaining study medication and rescue medication
- Review diary
 - Review time and date of each gel application
 - Review scores for Pain Intensity and Pain Relief
 - \circ Review rescued medication use.
- Collect Visit 3 subject diary
- Perform a general physical examination including vital signs

GlaxoSmithKline Consumer Healthcare Confidential Template Version Effective: 18-May-18 (CCR #11475) Page **37** of **64**

Diclofenac Diethylamine 2.32% Study 211206 Protocol Amendment 1

- Urine pregnancy test (women of child bearing potential only)
- Safety laboratory blood samples for chemistry and hematology. Any subject with a clinically significant abnormality will be followed until its resolution.
- POM, tenderness, ankle swelling, and ankle joint function (total score and subcategories) will be assessed
- Count and document remaining rescue medication

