8.3 Study Conclusion

The Study Conclusion page of the CRF will be completed for all subjects whether they completed all study procedures or if they were discontinued from the study early. If the subject discontinued early, at any point during the study, the primary reason for withdrawal should be recorded on the Study Conclusion page.

If a subject has any clinically significant, study-related abnormalities or AEs at the conclusion of the study, the GSK CH medical monitor (or designated representative) should be notified and, the subject may be asked to remain at the clinical site or be asked to return for a follow-up visit to ensure any issue is resolved or deemed not clinically significant.

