8.4 Follow-up Visit / "Phone Call"

The study site may contact a subject to follow up an AE post-study completion/withdrawal and, in some circumstances, request they return to the site for additional follow-up visits (final safety assessments). If needed, additional examinations may be carried out at such visits.

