9.3.1 Laboratory Tests

The following laboratory tests/analytical measures will be performed by appropriately trained staff/clinical examiners, at the times and in the order defined in the Study Procedures section of this protocol.

Hematology	Chemistry	Other		
Hemoglobin Hematocrit RBC count Platelet count WBC count Total neutrophils (Abs) Eosinophils (Abs) Monocytes (Abs) Basophils (Abs) Lymphocytes (Abs)	BUN/urea and Creatinine Glucose Calcium Magnesium Sodium Potassium Chloride Total CO2(Bicarbonate) AST, ALT Direct Bilirubin Indirect Bilirubin Total Bilirubin Alkaline phosphatase Uric acid Albumin Total protein PT/INR	Urine pregnancy test		

Table 9-1Laboratory Tests

Definitions: RBC= Red blood cell; WBC= White blood cells; BUN=Blood urea nitrogen; AST= transaminase; ALT= alanine transaminase; PT/INR= prothrombin time/ international normalized ratio.

Information on the local laboratory and sampling routines, normal ranges, and reporting will be provided in the Investigator binder supplied to each center. The local laboratory will report results to the center as early as possible in order to allow the Investigator to review the results no later than 24 hours after blood samples being taken.

Additional laboratory results may be reported on these samples as a result of the method of analysis or the type of analyzer used by the clinical laboratory; or as derived from calculated values. These additional tests would not require additional collection of blood. Unscheduled safety lab tests may be obtained at any time during the study to assess any perceived safety concerns.

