#### 3.3 Timepoints and Visit Windows

Before the study is unblinded, each actual post-baseline visit will be mapped to the target visit date to which it is chronologically closest. This corresponds to the following visit windows: Visit 2 (Days 2–4), Visit 3 (Days 4–6), Visit 4 (Days 7+). The numbering of the actual visits (from Visit 1 to Visit 4) will then be changed as needed to improve the correspondence of the actual visit dates to the protocol-specified schedule of visits, particularly in relation to Visit 3 (primary). Final determinations will also be made and documented before the study is unblinded to address visits that occur on Day 4 (which maps to two visit windows) or visits occurring well beyond the target date for the final visit or any other irregularities.

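### The last-record rule for laboratory tables lets a resolved repeat filed under Visit 4 replace the abnormal scheduled value, and the SAP does not clearly say that repeats are listed only

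*SAP*

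**What the plan says.** **Record selection.** SAP 4.7.2 sets the rule for both kinds of laboratory table: "For lab summary and shift tables, the last available record/value for a particular lab test for a subject at a particular visit" is the one analysed. The summary gives mean, SD, median, minimum and maximum by arm. Protocol 12.2.7 specifies shifts from Visit 1 to Visit 4.

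**Sampling.** Chemistry and hematology are scheduled at Visit 1 and at Visit 4 or early discontinuation (Protocol 1.1, SAP 4.7.2). Each subject therefore has one scheduled post-baseline value per test.

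**Repeats.** Protocol 8.2.3, on the Visit 4 samples, states: "Any subject with a clinically significant abnormality will be followed until its resolution". Under Protocol 8.3 a subject with a significant study-related abnormality at the end may "be asked to return for a follow-up visit to ensure any issue is resolved or deemed not clinically significant". Protocol 8.4 allows return visits to follow up an adverse event after completion or withdrawal. Protocol 9.3.1 adds: "Unscheduled safety lab tests may be obtained at any time during the study to assess any perceived safety concerns".

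**Visit assignment.** SAP 3.3 states that "each actual post-baseline visit will be mapped to the target visit date to which it is chronologically closest", with an open-ended Visit 4 window (Days 7+). Decisions are to be made before unblinding on "visits occurring well beyond the target date for the final visit or any other irregularities".

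**Listing.** SAP 4.7.2 lists all results, including those from unscheduled visits. After the last-record rule it returns to the subject: "In case there are some unscheduled tests (irrespective of schedule visit or not") are done for safety reasons, those are to be listed.

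**The concern.** A last-record rule is harmless when repeats are unrelated to the result. Here they are mostly triggered by it. A subject with an unremarkable Visit 4 value has little reason to be retested, while a subject with a clinically significant abnormality is retested until it has gone. The last record then tends to be the recovered value, so the rule leans towards fewer abnormalities.

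The summary and shift tables are the planned between-arm laboratory displays. If a recovered value stands in for the abnormal one, a laboratory adverse event could appear in the adverse-event tables with no matching shift and no matching extreme in the laboratory tables.

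**Working it through.** The plan states no figure on this point, and the sample-size calculation does not enter into it. The check is a reading of the text, followed by simple counts.

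**1. When the rule acts.** It changes a table only if a subject has at least two records for a test at one visit. With one scheduled post-baseline sample, the second Visit 4 record must be a repeat.

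**2. How a repeat could come under Visit 4.**
- *Recorded at the same visit.* The rule picks the later value, unless the listing sentence is taken to keep it out of the tables.
- *Through SAP 3.3.* If a return visit after Day 8 counts as an actual post-baseline visit, Days 7+ places it in Visit 4. The text does not say that it counts as one.

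**3. Two readings of SAP 4.7.2.**

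| Reading | Scheduled abnormal value in the tables? |
|---|---|
| Unscheduled repeats are listed only | Kept; at most, some repeats logged as Visit 4 records are affected |
| Unscheduled repeats are listed and also eligible for the tables | Replaced by any later repeat filed under Visit 4 |

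**4. Effect on one subject (assumed values).** ALT is 0.5 x ULN at Visit 1, 4.0 x ULN at the scheduled Visit 4 sample and 0.8 x ULN at a repeat filed under Visit 4. The last-record rule tabulates 0.5 to 0.8: no shift, and 4.0 is absent from the arm's maximum. The scheduled sample gives 0.5 to 4.0, a shift from normal to high. A low abnormality would affect the minimum in the same way. The arm's extreme changes only if this subject held it.

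**5. Effect on counts.** The plan randomizes 300 subjects, so 300/2 = 150 per arm. Let k be the number with an abnormal scheduled Visit 4 value. The documents give no k, so a range is shown.

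| k | Shifts, scheduled sample | Shifts, every abnormal value replaced by a resolved repeat |
|---|---|---|
| 1 | 1/150 = 0.7% | 0 |
| 2 | 2/150 = 1.3% | 0 |
| 3 | 3/150 = 2.0% | 0 |
| 5 | 5/150 = 3.3% | 0 |

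**6. Effect on the by-arm maximum.** Suppose that k subjects in one arm have rises above every background value, that each is independently replaced with probability f, and that the arms are otherwise alike. All k are lost with probability f^k, and the higher maximum is then a coin toss. So P(affected arm shows the higher maximum) = (1 - f^k) + 0.5 f^k = 1 - 0.5 f^k.
- f = 0: 1.00 for any k.
- f = 0.5: 1 - 0.5(0.5) = 0.75 for k = 1; 1 - 0.5(0.125) = 0.94 for k = 3; 1 - 0.5(0.03125) = 0.98 for k = 5.
- f = 1: 0.50 for any k.

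A simulation with assumed log-normal ALT (median 0.5 x ULN, between-subject log-SD 0.41, within-subject log-SD 0.20, rises to 3 to 5 x ULN) gave 0.752, 0.939 and 0.984 at f = 0.5. The agreement shows that the answer is essentially the assumed f and k. It is not evidence of what f is in this trial.

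**7. Early-discontinuation samples.** SAP 4.7.2 labels this sample as Visit 4. SAP 3.3, read literally, would renumber a termination visit on Days 2 to 6 as Visit 2 or 3, outside the Visit 1 to Visit 4 shift. The laboratory-specific label should prevail, but the SAP does not say so.

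**The case against.** The strongest reply is that SAP 4.7.2 already settles the matter. Its paragraph first says that every result is listed, so a second sentence on listing unscheduled tests adds something only if it means listing instead of tabulation. Its wording ("In case there are some unscheduled tests (irrespective of schedule visit or not") seems to reach repeats at a scheduled visit too. The last-record rule would then serve only for redrawn or corrected samples. This is a fair reading, and may be the intended one. It is not conclusive: the sentence does not say that unscheduled tests are excluded from the tables, and if it did exclude them the rule above it would have little left to do.

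The second reply concerns the window. A reader might infer that any late return visit, say on Day 10, automatically becomes Visit 4 and overwrites Day 8. The documents do not support that. SAP 3.3 renumbers Visits 1 to 4 to fit the protocol schedule, chiefly for the primary visit. Under Protocol 8.4 the site may "request they return to the site for additional follow-up visits (final safety assessments"), which places such visits outside that series, and late visits are decided before unblinding. What remains is that no criterion is given for laboratory repeats.

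Third, a reader might infer that subjects withdrawn at Visit 2 for laboratory abnormalities represent hidden drug effects. They do not: Protocol 8.2.1 concerns the Visit 1 results, and Protocol 4.3 has those samples taken before randomization.

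Fourth, the course is 7 days of topical treatment, and Protocol Section 2 puts systemic absorption of topical NSAIDs at 3-8% of oral. Nothing in the documents leads one to expect ALT rises of 3 to 5 x ULN. That stands, and it limits the expected size.

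**Conclusion.** The point holds as a minor one. SAP 4.7.2 states a last-record rule that, applied to repeats made because a result was abnormal, can put a resolved value in place of the abnormal scheduled one. The displays affected are the shift table and the by-arm minimum or maximum. It requires that the repeat be filed under Visit 4 and that unscheduled repeats not be confined to listings; the SAP leaves the second open.

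The size is one lost shift, 0.7% of a 150-subject arm, for each affected subject. How many there will be is unknown and may be zero, and the figures for k and f above are assumptions.

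A reader might go further and conclude that the safety assessment is compromised. The documents do not support that. The safety endpoint is adverse events, clinically significant laboratory abnormalities meet the adverse-event definition (Protocol 10.1) and are tabulated by arm (SAP 4.7.1), and every value is listed. The primary conclusion is unaffected.

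**What to change.** Replace the last-record sentence in SAP 4.7.2 with four statements:

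1. All by-visit statistics and the Visit 1 to Visit 4 shift table use the first valid scheduled Visit 4 or early-discontinuation sample. A repeat replaces it only if the first sample was documented as invalid before unblinding.
2. The renumbering in SAP 3.3 does not apply to laboratory samples, so early-discontinuation samples remain Visit 4.
3. Other repeats are listed and do not enter these by-visit tables.
4. A separate table shows the shift from baseline to the worst post-dose value, unscheduled tests included. For analytes where both directions matter, such as sodium, potassium, glucose and white cell count, the lowest and highest values are taken separately.

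Keeping the worst value in its own table means that the mean and the maximum in the by-visit summary come from the same records, and that summary stays as Protocol 12.2.7 describes it.

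The cost is a few sentences, a change to record selection and one extra display. No new data are needed. The worst-value table will show slightly more trivial crossings in subjects who were tested more often, so it should be read beside the by-visit shift.
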